#### Interim efficacy analyses

Two interim analyses are planned at the end of stage 1: the first for efficacy and the second for futility. For both analyses only the experimental treatments considered « safe » at first stage will be tested against the control arm. For the efficacy analysis the Haybittle–Peto boundary will be used as stopping rule (Haybittle 1971): if a probability  $\leq 0.001$  that a

difference as extreme or more as that observed at the interim analysis, between the treatments is found, given that the null hypothesis is true, then the trial should be stopped early for efficacy. In case of the probability will be greater than 0.001 the trial will continue with the stage 2 and the final analysis will be still evaluated at the level of significance without alpha error correction. The interim analysis for futility will be performed according to the conditional power analysis (Lachin 2005). The experimental arm will be stopped if, under the assumption of the results distribution of future data, calculated assuming the current trend or the alternative hypothesis, the probability of detect a statistically significant results at the end of the trial will be <20%.

**Step 2:** final efficacy analysis.

Each experimental arm passing the step 1, will be compared with control arm at a statistical significant level of 0.025, one side. In this way, in case that both arms are considered for the efficacy comparison, the statistical significant level will be set to 0.025, 1 side, in order to preserve an overall family wise error of 0.05. Primary endpoint will be the difference in viral load decline from baseline to 7 days. Viral load will be measured as  $\log_{10}$  of genome copies per mL, ascertained by Digital Droplet quantitative PCR (DD-PCR). In order to calculate the sample size, we refer to data recently published on Lancet Inf. Dis. (To 2020), showing that in a population with mild disease presentation, the difference in mean viral load from baseline to 7 days is 1.05  $\log_{10}$  copies per mL (from 0.77 to 1.33  $\log_{10}$  copies, calculated from the slope and its 95%CI), with an estimated SD=0.69  $\log_{10}$  copies per mL. The desired difference in decrease between each experimental group and control is at least 0.47  $\log_{10}$  copies per mL in order to detect an effect size  $\Delta = 0.68$  (considered to be of moderate-large magnitude according to Cohen 1988). According to these hypotheses, with 34 pts per arm the study has a power=80% to detect a statistically significant difference between the experimental vs. control arm, at 0.025 alpha level, one side.

Therefore, if both experimental treatments will be compared with control group, the total number of patients to be analyzed will be 102. Considering a potential 20% loss to follow-up, it is planned to enroll 129 patients.

If only one experimental group is compared with control arm, the total number of evaluable patients will be 84 (105 to be enrolled).

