## **STUDY DESIGN**

This is a multicentre, prospective, randomized, double-blind, adaptive phase II dose finding study.

Patients meeting the inclusion criteria will be asked to participate to the study and randomized in a 1:1:1 ratio to either:

- Placebo arm (arm A): placebo will be identical in appearance to ivermectin in order to preserve blinding and will be administered p.o. at empty stomach with water once daily, for 5 days

- Intervention arms: a) Ivermectin, single dose 600 µg/kg, for 5 days (I\_600) and placebo (arm B) ; b) Ivermectin, single dose 1200 µg/kg, for 5 days (I\_1200) (arm C) ); these drugs will be administered p.o. once daily, for 5 days.

In arm A and B, the number of placebo tablets to be administered will be calculated by the study dedicated pharmacist considering the number of tablets that should be taken in case a patient with the same weight is assigned to arm C.

[figure not shown]
Patients will be randomized by a centralized computer system. At randomization a treatment ID is assigned to the patient. Once a treatment ID is assigned this must not be re-assigned even in cases of errors.

Enrolled subjects will be identified by a unique subject number (patient code) that will remain consistent for the duration of the study.

Patients will be recruited at the emergency room of hospitals, and/or among asymptomatic hospital workers found positive for SARS-CoV-2 at routine screening and/or in outpatient ambulatory settings, and/or at home, if not meeting the clinical criteria for hospitalization, according to the routine procedure of each participating site. The expected duration of subjects inclusion in the study is of 3 months, or until the planned number of subjects to be enrolled will be reached.

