## ***Random allocation procedure***

Patients will be randomly assigned to one of the three treatment groups with an equal probability of assignment to each treatment (allocation ratio 1:1:1). The study biostatistician will prepare the sequence of treatments according to a randomized permuted blocks procedure and the randomized list will be centralized. The randomization list will be generated using SAS 9.4 release. The randomised allocation of treatment ID will be centralised.

Upon recruitment of a patient meeting the inclusion criteria, the local investigator will follow an online procedure (detailed in the Manual of Procedures) to know the treatment ID of the patient. After randomization the treatment ID, along with patient's weight and patient code, will be transmitted to the hospital pharmacist who is in charge to prepare the study treatment according to randomization arm.

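### Testing both doses at a fixed one-sided 0.025 is valid but spends the stated 0.05 inefficiently; a Holm step-down would gain about 6 to 10 points of power for both doses with no extra patients

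*Protocol*

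**What the plan says.** The Study Design section calls the trial an "adaptive phase II dose finding study", with two ivermectin doses and one placebo arm randomised 1:1:1. Step 2 of Statistical design and sample size sets the final test: "Each experimental arm passing the step 1, will be compared with control arm at a statistical significant level of 0.025, one side". The reason follows for the case where both doses are tested: "the statistical significant level will be set to 0.025, 1 side, in order to preserve an overall family wise error of 0.05".

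The sample size rests on a per-dose target, "The desired difference in decrease between each experimental group and control is at least 0.47" log10 copies per mL, "with an estimated SD=0.69", and concludes that "with 34 pts per arm the study has a power=80% to detect a statistically significant difference between the experimental vs. control arm". With three arms, "if both experimental treatments will be compared with control group, the total number of patients to be analyzed will be 102".

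No step-down is described, and no power is given for showing that both doses work. The interim rules (efficacy stop at 0.001, futility stop at conditional power below 20%) leave the final significance level uncorrected.

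**The concern.** The rule holds each dose at 0.025 whatever the other dose shows. Once one dose has been declared effective at 0.025, the other can be tested at one-sided 0.05 and the family-wise error still stays within 0.05. Under the written rule, a second dose with a p-value between 0.025 and 0.05 is called negative, although the sponsor's own error limit would allow it to be declared.

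This matters because the trial is meant to inform dose choice, so the status of each dose counts, and not only whether some dose works. The lower dose could look ineffective beside a successful higher dose when both have an effect. The level is fixed in the protocol with its rationale, so it is not a detail left to an analysis plan.

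**Working it through.** **Inputs** (Step 2, with allocation from Random allocation procedure): 34 per arm, difference 0.47, SD 0.69, one-sided 0.025 per dose, family-wise 0.05, 1:1:1 with a shared placebo arm. Assumed: both doses pass the safety step and both have a true difference of 0.47.

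**1. The printed 80%.** Standardised difference: 0.47 / 0.69 = 0.681. Expected test statistic: 0.47 / (0.69 × √(2/34)) = 2.808. Normal power: Φ(2.808 − 1.960) = 0.802. The exact noncentral t test gives 0.790, and the normal formula for 80% power returns 34 per arm. The figure reproduces.

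**2. Correlation of the two tests.** With equal arms, the shared control contributes σ²/n of each comparison's 2σ²/n, so the correlation is 0.5.

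**3. Written rule, normal approximation.** Let B(a, b) be the probability that the two statistics exceed a and b.
- Both doses: B(1.960, 1.960) = 0.690.
- At least one: 2 × 0.802 − 0.690 = 0.914.

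**4. Holm.** The smaller p-value must be at most 0.025 and the larger at most 0.05 (critical value 1.645), with B(1.960, 1.645) = 0.73956.
- Both doses: 2 × 0.73956 − 0.68980 = 0.789.
- Per dose: 0.80193 + 0.73956 − 0.68980 = 0.852.
- At least one: unchanged at 0.914, because the first step is still at 0.025.

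**5. The same with t tests** (simulation, 400,000 trials of 34 per arm):

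| Quantity | Fixed 0.025 | Holm |
|---|---|---|
| Power per dose | 79.0% | 84.3% |
| Power for both doses | 67.4% | 77.9% |
| Power for at least one | 90.6% | 90.6% |
| Any false rejection, no dose works | 4.5% | 4.5% |
| False declaration of the inactive dose, other at 0.47 | 2.5% | 5.0% |

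If the lower dose has only half the effect, its power rises from 28.2% to 38.5% (separate simulation, 240,000 trials).

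**6. Allowing for the interim rules** (look at 20 of 34 per arm; conditional power calculated at the 0.025 level). Power for both doses:

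| Interim handling | Fixed 0.025 | Holm | Gain (points) |
|---|---|---|---|
| No interim stopping | 67.4% | 78.0% | 10.5 |
| Futility, alternative hypothesis | 67.0% | 76.9% | 10.0 |
| Futility, current trend | 61.6% | 68.4% | 6.8 |
| Whole trial stops at 0.001, no futility | 51.5% | 61.0% | 9.5 |
| Whole trial stops at 0.001, futility on alternative | 51.1% | 60.1% | 9.0 |
| Whole trial stops at 0.001, futility on trend | 45.9% | 51.9% | 5.9 |

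In the last three rows a second dose counts after an early stop only if it also crosses 0.001. With both doses effective, at least one crosses that bound at the interim in 23% of trials.

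**The case against.** The strongest reply is that nothing here is wrong. Bonferroni is a standard rule, its purpose is stated and the power figure reproduces. That stands. A reader might infer from 67% and 80% that the trial is underpowered or that its power statement is false. The protocol does not support this. The 80% is given for one experimental arm against control, the second primary objective concerns whichever dosage or dosages are found safe, and power for both doses is never promised. The chance that at least one dose succeeds is 91%, and Holm does not alter it.

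Second, the gain has a price. If only one dose works, Holm doubles the chance of wrongly declaring the other, from 2.5% to about 5%, and a false declaration also distorts dose choice. This stands as a trade-off. A sponsor who wanted 0.025 per dose for its own sake could decline, but the protocol gives family-wise 0.05 as the reason, and Holm meets that limit.

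Third, 67% and 78% assume that interim looks change nothing. This also stands: the absolute figures fall under the stopping rules, although Holm stays ahead in every case examined.

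Fourth, keeping 0.025 when only one dose remains leaves part of the 0.05 unused there, so a dose tested alone faces a stricter level than one tested after its companion succeeds. That is true. But Holm releases 0.05 only after a rejection, not because an arm was dropped, so keeping the existing 0.025 is the safe choice.

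**Conclusion.** The point holds as an avoidable inefficiency in a rule that the protocol has already fixed. It is neither an arithmetic error nor a contradiction. If both doses have a true difference of 0.47, both reach the final analysis and no interim stopping occurs, Holm adds about 5 points of power per dose (79% to 84%) and about 10 for both doses (67% to 78%). With the interim rules applied, the gain for both doses is about 6 to 10 points. If only one dose reaches the final analysis, nothing is gained.

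Family-wise error at the final test is at or below 5%. The uncorrected 0.001 look adds little: with no dose effective, the written rule gives 4.6% with it. In the extreme case of one overwhelmingly effective dose and one inactive dose, Holm with the look gives 5.0 to 5.1%.

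It would be wrong to say that Holm recovers power the protocol had claimed, because no figure for both doses was claimed. The change is desirable but optional.

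**What to change.** In Step 2, replace the fixed level for the two-dose case with a Holm procedure: when both doses reach the final analysis, test the smaller p-value at one-sided 0.025 and, only if it is significant, test the other dose at one-sided 0.05. If only one dose remains, keep 0.025. State that the 80% is power per comparison; giving the power for both doses and for at least one beside it would help.

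Two interim details need a sentence each. First, conditional power for futility should be calculated at the 0.025 level, because under Holm the final level otherwise depends on the other arm. Second, the plan should say how the second dose is tested if the first crosses 0.001 at the interim.

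The cost is a few sentences in the protocol and analysis plan, written before unblinding. The 34 per arm, 102 evaluable and 129 enrolled do not change, because the first Holm step keeps the 0.025 level. Two downsides should be accepted openly: the higher chance of declaring an inactive second dose, and the fact that simple one-sided 97.5% confidence limits will no longer match every decision, since the second dose may be declared at a nominal p-value of up to 0.05.

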## **Secondary outcomes**

1. Trend over time of quantitative viral load at Day 7, 14 and Day 30 as measured by quantitative, digital droplet PCR.
2. Time to clinical resolution (for symptomatic patients).
3. Proportion of patients with virological clearance at day 14 and 30
4. Rate of hospitalization.
5. COVID-19 Severity Score at Day 14 and Day 30

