## **Analysis of the primary outcome**

The proportion of patients in each experimental group experiencing at least one SADR will be described by means of frequency and percentages.

The mean of the differences in viral load decline from baseline to 7 days between each experimental group and the control group will be described by standard summary measures for continuous data and compared by mean of Student T test or the equivalent non parametric method (according to the Barlett's test for homogeneity of variances).

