### **Analysis of the secondary outcomes**

Binary outcomes will be described by frequencies and proportions and summarised by mean of absolute and relative difference, with their relative 95% CI. Mantel Haenzel test will be used for pairwise comparison between groups. For expectedly rarer outcomes (such as deaths, patients with blood test alterations during treatment), Fisher's exact test will be used if required.

Continuous variables will be first assessed with Barlett's test for homogeneity of variances. Then, the t-test for comparing two means or the Wilcoxon rank sum for non-normal populations, whichever the more appropriate, will be used.

The pattern of compliance to treatment will be explored and compliers/non compliers will be compared with respect to baseline demographic and clinical data.

Time to clinical resolution (TCR) will be calculated as the time from randomisation to clinical resolution or death. A competing risk model will be used to analyze TCR, since the death is considered as competing event.

The assessment of safety profile will be mainly based on adverse reactions (ARs) and the frequency and nature of SAEs.

For each patient and for each type of adverse event, the worst degree ever suffered during treatment will be used for the analysis. All safety parameters will be presented and analyzed in terms of listings and summary tables.

The proportion of patients in each group experiencing adverse events will be compared through the chi-square test (or the Fisher's exact test when appropriate).

SAEs will be summarized by presenting the number and percentage of patients having any SAE. Other information collected (e.g. severity or suspected relationship to study medication) will be listed as appropriate.

Generalized longitudinal mixed models will be used to analyze the trend over time of viral load at different time points (baseline, 7 days, 14 days, 30 days).

Multiple regression will be used to study the variation of main random variables according to several potential predictor variables including among others: age; sex; continent of origin; recruiting centre; test results on recruitment.

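### The primary t test on log10 viral-load decline, and its 80% power, assume every Day 7 value is measurable; undetectable swabs force exclusion or substitution, and power then falls with their share

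*Protocol*

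**What the plan says.** Step 2 of the protocol's section on statistical design and sample size defines the endpoint: "Primary endpoint will be the difference in viral load decline from baseline to 7 days", on the log10 copies per mL scale, measured by digital droplet PCR. Each experimental arm is compared with control "at a statistical significant level of 0.025, one side". The planning values are a control decline of 1.05 and an SD of 0.69, and "The desired difference in decrease between each experimental group and control is at least 0.47" log10 copies per mL. From these the section concludes that "with 34 pts per arm the study has a power=80" per cent.

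The section on analysis of the primary outcome says the declines are "compared by mean of Student T test or the equivalent non parametric method", with Bartlett's test of equal variances deciding between the two. For the later time points, "Generalized longitudinal mixed models will be used to analyze the trend over time of viral load".

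Eligibility requires a positive RT-PCR and sets no minimum viral load. Asymptomatic hospital workers found positive at routine screening may be recruited (Study Design). Negative swabs are foreseen: a secondary outcome is "Proportion of patients with virological clearance at day 14 and 30", and Routine visits says what to do if the Day 14 swab is negative. The protocol gives no detection limit and no expected share of undetectable samples at Day 7. It does say that a full SAP will be written before analysis.

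**The concern.** A decline in log10 load is a subtraction that needs a number at Day 7. If no virus is detected, all that is known is that the load lies below the assay's limit. A t test, or a rank test on declines, cannot use that information. Either the patient is left out or a value is supplied.

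Take a patient with 3 log10 at baseline and an assumed limit of 2 log10. Substituting the limit records a decline of exactly 1.0, however far the load really fell. Substituting 0 log10 records 3.0. Leaving the patient out removes someone because the virus could no longer be detected.

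If the drug works as planned, more patients reach the floor in the active arm, so the distortion is not balanced between arms. The protocol's trigger for the non-parametric option, unequal variances, does not look for a floor.

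The power of the main comparison is at stake. So are the interim decisions, if the same comparison feeds the 0.001 efficacy boundary and the rule that stops an arm when conditional power is below 20%. An attenuated difference at 20 patients per arm makes a futility stop of an active arm more likely.

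**Working it through.** **1. The protocol's own figure.** Inputs from Step 2: difference 0.47, SD 0.69, one-sided alpha 0.025, power 80%.

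n = 2 × (1.960 + 0.842)² × (0.69/0.47)² = 2 × 7.85 × 2.155 = 33.8, so 34 per arm. The normal approximation gives 80.2% power at 34. The t distribution gives 79.0%: non-centrality 0.47 / (0.69 × √(2/34)) = 2.81 on 66 degrees of freedom. Enrolment also reproduces: 34/0.8 = 42.5, so 43 per arm and 43 × 3 = 129. The arithmetic is right provided every Day 7 value is observed.

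**2. Inputs the protocol does not give (assumed).** Baseline load is normal with SD 1.5 log10, truncated at the detection limit. The limit and baseline mean are varied to give a range of undetectable shares. The decline is N(1.05, 0.69) in control and N(1.52, 0.69) in the active arm (1.05 + 0.47). A Day 7 sample is undetectable if baseline minus decline is at or below the limit.

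**3. Power under each way of making the t test run.** For each handling, the resulting mean difference and pooled SD enter the same non-central t with 34 per arm, or fewer when patients are excluded. The uncensored reference is 79%.

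| Limit / baseline mean (log10) | Undetectable, control v active | Excluded | Set to limit | Set to 0 |
|---|---|---|---|---|
| 2 / 6.5 | 2% v 3% | 77% | 78% | 75% |
| 2 / 5.5 | 6% v 11% | 73% | 74% | 70% |
| 2 / 4.5 | 15% v 24% | 66% | 65% | 64% |
| 2 / 3.5 | 28% v 41% | 55% | 50% | 59% |

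Repeat runs agree with these entries to within about two points. The set-to-0 column also depends on the limit itself: at limit 1 and baseline mean 5.5 (again about 2% of controls) it gives 78%, while at limit 3 and baseline mean 5.5 (15% of controls) it gives 53%.

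**4. Where the loss comes from (limit 2, baseline mean 4.5).**
- Excluded: the difference falls from 0.47 to 0.43, and numbers shrink.
- Set to limit: the difference falls to 0.38.
- Set to 0: the difference rises to 0.56, but the SD rises from 0.69 to 0.98. Non-centrality is 0.56 / (0.98 × √(2/34)) = 2.36, against 2.81 in step 1.

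**5. A second set of assumptions.** Here the limit is chosen to fix the control share, and the baseline SD runs from 0.5 to 2.0. Substituting the limit gives power of 73–77% at 5% of controls undetectable, 66–75% at 10%, 53–68% at 20% and 41–58% at 30%. At 20%, half the limit gives 61–73%, exclusion 46–65%, and a rank test on limit-substituted declines 48–64%. The non-parametric option does not restore the power.

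**6. The alternative.** A Tobit regression of Day 7 log10 load on arm and baseline load, left-censored at the limit, recovers an effect of about 0.47 in the scenario of step 4, with power of about 75%. Across the scenarios run, its power is about 72–78%. Its one-sided type I error was 2.3–3.7% against a nominal 2.5%. When only about 2% of controls are undetectable it gives up nothing material.

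**The case against.** The strongest reply is that coding an undetectable PCR result is ordinary SAP content. The protocol announces an SAP, so a missing coding rule is not an error in the protocol. That stands, and the point does not rest on it. The protocol itself fixes the endpoint, the test and the power basis. A coding rule added later that keeps the named test still lost power in nearly every scenario; recovering it needs a different model.

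Four stronger readings are tempting, and the documents do not support them.
- *That the written analysis discards or caps the best responders.* No section prescribes dropping, capping or substituting. Efficacy is by intention to treat with all randomised subjects included, which points against dropping. Those who reach the floor also include patients with a low starting load and a modest decline.
- *That the stated power is not delivered.* It reproduces from its own inputs, and the loss is close to nil if few Day 7 samples are undetectable. Evidence on that share is indirect: clearance is an outcome at Days 14 and 30, not Day 7.
- *That the effect is always shrunk.* Substituting 0 log10 enlarges it; the harm there is the larger SD.
- *That false positives increase.* With no drug effect, both arms have the same expected share at the floor.

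It is also fair that the Tobit results come from data generated largely under the model's own assumptions, so its advantage in practice may be smaller.

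**Conclusion.** The point holds in a conditional form. The protocol's test cannot use an undetectable Day 7 result without exclusion or substitution, and 34 per arm makes no allowance for this. The stated 80% power therefore holds only if few Day 7 samples are undetectable.

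Under the assumed baseline SD of 1.5 log10 and a limit of 2 log10, power is roughly 75–79% at 2% of controls undetectable (77–79% if set-to-0 is left aside), 68–75% at 6%, 62–66% at 15% and 50–60% at 28%. The direction was the same under the other baseline spreads tried; the size cannot be fixed from the protocol. This is a matter of power and of attenuation or added variance, not of type I error. The change is worth making because it costs little and protects against a loss that could be large.

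**What to change.** In Step 2 and in the analysis of the primary outcome, replace the t test on declines with a left-censored normal (Tobit) regression of Day 7 log10 copies per mL on arm and baseline log10 load, censored at the digital droplet PCR detection limit. In addition:

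- Give the detection limit, and state that an undetectable result is an observed outcome: never missing, never 0 log10.
- Use the same statistic for the interim efficacy and futility rules, and fix it before the interim analysis is unblinded.
- Apply the same left-censoring in the longitudinal mixed model. If the planned control decline stayed linear, it would reach 2 × 1.05 = 2.1 log10 by Day 14 and 30/7 × 1.05 = 4.5 by Day 30, so censoring is likely to be heavier there.
- Add a rank test with undetectable values tied at the best rank as a sensitivity analysis. It checks the distributional assumption and should not be expected to restore power.
- State that the 80% power assumes few undetectable Day 7 samples, and show power over a stated range of that share.

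The cost is wording and a standard procedure; no patients, swabs or data are added. The model relies on approximate normality of log10 load, much as the t test does for the decline. With about 34 per arm, a likelihood-ratio test with a t reference, or a permutation check, is advisable.
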